6.3. Intervention – Procedural (if applicable)

Description: [N/A

Training on Procedural Intervention: N/A

6.4. Concomitant Therapy (if applicable)

N/A

6.5. Rescue Medications and Procedures (if applicable)

N/A

6.6. Compliance Checks

N/A

6.7. Withdrawal / Discontinuation of Enrolled Participants

Patient's participation will be discontinued if:

1. Subject develops new or worsening respiratory symptoms including shortness of breath or decrease in FEV1 of 20% or greater.
2. Subject develops a condition that is an exclusion criterion.
3. Subject is noncompliant with the recommended withholding of SABA or ICS/LABA for 12 hours prior to study.

If any of the above are met, then patient will not continue.

6.8. Voluntary Withdrawal (Drop-Out) of Enrolled Participants

Participants may voluntarily withdraw participation at any time, for any reason, with no penalty or loss of rights. Patients will not require follow up if they withdraw and can continue routine medical care.

7. Study Procedures and Schedule

7.1.Table of Events

| Procedures | | MCC Visit (Day 1) |
|--------------------------------|------------------|----------------------|
| Informed Consent | | X |
| Medical History, med review | | X |
| Concomitant Medications | | X |
| COVID-19 Screen | | X |
| Physical Exam | Complete | X |
| | Symptom-Directed | X |
| | Vital Signs | X |
| Urine Pregnancy Test | | X |
| Spirometry | | X |
| MCC | | X |

7.2.Pre-Screening / Screening

Subjects will be screened by phone for potential eligibility and interest once they are identified using the recruitment strategies discussed in Section 5.3. Screening will review inclusion and exclusion criteria.

Approximately 48 hours before the study visit, subject will be screened for COVID-19 using the screening questions stated in section 7.4 and reminded to withhold use of SABA or LABA 12 hours prior to visit, and airway clearance medications (e.g. Hypertonic Saline or Pulmozyme) for 24 hours before the visit.

7.3.Enrollment / Baseline (Day 0)

On the day of the study, medical history and exclusion criteria will be reviewed again. Consent will also be signed on day of the study.

7.4. Study Visits

Intervention/Treatment procedures for MCC (by visits)

Adverse events are assessed at each visit.

Screening Call: Approximately 48 hours before the study, patient will undergo a COVID-19 screen with the questions below:

Do you feel feverish or have a fever?

Do you have a new or worsening cough?

Do you have a new or worsening sore throat?

Are you newly short of breath?

Have you had a new onset of loss of taste or smell in the last 5 days?

Do you have new onset vomiting or diarrhea?

Do you have new onset of repeated shaking with chills not related to another medical condition?

If patient answer yes to any of the questions above, study will be cancelled.

MCC/Treatment visit: On day of the study, medical history will be updated, including any new medications or new medical history. Vital signs and baseline spirometry will be collected, and a negative urine pregnancy test will be required for all women.

Participants will inhale aerosolized radiolabeled sulfur colloid (Tc99m-SC) and will undergo gamma scintigraphy to measure mucociliary and cough clearance (MCC/CC) of the radiolabeled particles from the airways. During the first hour of MCC imaging patients will attempt to avoid coughing. Subjects will then inhale 4 puffs of albuterol (90 mcg/puff via metered dose inhaler (MDI) with spacer) to assess the effect of beta-adrenergic stimulation on MCC over the second hour of MCC imaging. After the two hours of MCC imaging, patients will perform spirometry and directed coughing over a 30-minute period during which cough clearance will be measured, again by gamma scintigraphy. Subjects will then rest (app 3.5 hours) and be scanned for 15 minutes at 6 hour (\pm 30 minutes) post initial MCC/deposition scan.

All personnel performing aerosolizing procedures (MCC scans and spirometry) will wear eye protection and N95 masks. A HEPA filter will also be placed in the room where the mucociliary scans will be performed.

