| | Key Exclusion Criteria 
1. Clinically severe disease (requiring oxygen; FEV1<30%)2. Currently smoking or vaping3. Radiation exposure in the past year that would cause them to exceed federal radiation safety guidelines4. Free of sino-nasal pulmonary exacerbation for 4 weeks. |
| Numbers of Participants | Number to be recruited for screening : 40 Number of eligible participants enrolled: 32 |
| Clinical Phase | I |
| Intervention | Short acting beta agonist inhaler (albuterol by metered dose inhaler) |
| Study Description | Participants will inhale aerosolized radiolabeled sulfur colloid (Tc99m-SC) and will undergo gamma scintigraphy to measure mucociliary and cough clearance (MCC/CC) of the radiolabeled particles-from the airways. During the first hour of MCC imaging subjects will attempt to avoid coughing. Subjects will then inhale 4 puffs of albuterol (90 mcg/puff via metered dose inhaler (MDI) with spacer) to assess the effect of beta-adrenergic stimulation on MCC over the second hour of MCC imaging. After the two hours of MCC imaging. Subjects will perform spirometry and directed coughing over a 30-minute period during which CC will be measured, again by gamma scintigraphy. Subjects will then rest (approximately 3.5 hours) and be scanned for 15 minutes at 6 hour post initial MCC/deposition scan. |
| Outcome Measures | Baseline MCC: Ave60Clr Change in MCC following albuterol: Ave120Clr-Ave60Clr Change in MCC following cough clearance: Ave150Clr-Ave120Clr |
| Study Duration | The entire study is expected to last up to 4 years. |
| Subject Participation Duration | Each subject's participation will last 1 day. |
| Estimated Time to Complete Enrollment | 4 years |

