4.1 Treatment Design

Type of Design: Open label; two group study with healthy controls

Screening/Baseline: Participants will undergo a general medical screening visit to include vital signs, physical exam and pregnancy test (if applicable), then proceed with spirometry.

Intervention/Treatment

Participants will inhale aerosolized radiolabeled sulfur colloid ($Tc99m$ -SC) and will undergo gamma scintigraphy to measure mucociliary and cough clearance (MCC/CC) of the radiolabeled particles from the airways in both groups. During the first hour of MCC imaging patients will attempt to avoid coughing. Patients will then inhale 4 puffs of albuterol (90 mcg/puff via metered dose inhaler (MDI) with spacer) to assess the effect of beta-adrenergic stimulation on MCC over the second hour of MCC

imaging. After the two hours of MCC imaging patients will perform spirometry and directed coughing over a 30 minute period during which CC will be measured, again by gamma scintigraphy. Subjects will then rest (app 3.5 hours) and be scanned for 15 minutes at 6 hour \pm 30 minutes post initial MCC/deposition scan.

Table of procedures

| PCD MCC/CC study flow sheet | minutes needed | cumulative min |
|---|----------------|----------------|
| 1 Vital signs, PE,pregnancy test, PFT | 30 | 30 |
| 2 Put Americium fiducial markers on | 5 | 35 |
| 2 Co57 Transmission scan | 5 | 40 |
| 3 Background scan | 15 | 55 |
| 4 Radioaerosol inhalation | 5 | 60 |
| 5 MCC scan (no cough) | 64 | 124 |
| 6 Albuterol MDI (4 puffs with spacer) | 6 | 130 |
| 7 MCC scan post albuterol | 54 | 184 |
| 8 PFT and directed coughing (30 coughs including any spontaneous induced by PFTs) | 20 | 204 |
| 9 CC scan post PFT/cough | 4 | 208 |
| 10 Rest until final scan 6 hours after beginning of #5 | 210 | 418 |
| 11 6 hour post initial radioaerosol MCC scan | 15 | 433 |

Unscheduled Visits: There is no expectation for unplanned visits. Subjects will simply be rescheduled if they have a change in health.

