5.2. Eligibility

Inclusion Criteria for PCD Patients

1. Age 12-90 of both genders

2. Confirmed PCD diagnosis with identified genetic mutations.
3. Negative pregnancy test for females who are not s/p hysterectomy with oophorectomy.
4. FEV1 of at least 30% of predicted.

Inclusion Criteria for Healthy Controls:

1. Age \geq 18 years old.
2. Subjects must have an FVC, FEV1 and FVC/FEV1 of at least 80% of predicted. Subjects who fall out of the normal range will be offered a copy of the test to share with their personal physician.
3. No pre-existing lung disease (asthma, cystic fibrosis, etc.).
4. Negative pregnancy test for females who are not s/p hysterectomy with oophorectomy.

Exclusion Criteria for all participants:

Clinical Contra-indications:

1. Any chronic medical condition considered by the PI as a contraindication to the exposure study including significant cardiovascular disease, diabetes, chronic renal disease, chronic thyroid disease, immunodeficiency, history of tuberculosis
2. Any acute infection requiring antibiotics within 4 weeks of study.
3. Mental illness or history of drug or alcohol abuse that, in the opinion of the investigator, would interfere with the participant's ability to comply with study requirements.
4. Medications which may impact the results of the study treatment, or may interfere with any other medications potentially used in the study (to include steroids, beta antagonists, non-steroidal anti-inflammatory agents)
5. Active smoking to include e-cigarettes within 1 year of the study, or lifetime of > 10 pack years of smoking
6. History of vaping or current vaping.
7. Allergy/sensitivity to study drugs, or their formulations.
8. Viral upper respiratory tract infection within 4 weeks of challenge.
9. Radiation exposure history in the past year which would be outside the safe levels
10. **Pregnant or lactating women** will also be excluded since the risks associated with radiation are unknown and cannot be justified
11. Use of the following medications:
 - a. Use of beta blocking medications
 - b. Receipt of LAIV (Live Attenuated Influenza Vaccine), also known as FluMist, within the prior 30 days, or any vaccine within the prior 5 days
 - c. Multivitamins, Vitamin C or E or herbal medications in the 4 days prior to the treatment visit
 - d. Non-steroidal anti-inflammatory drugs in the 4 days prior to the treatment visit.
12. Known IgE mediated hypersensitivity to albuterol

13. Physical/laboratory indications:

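### Participants are asked to avoid coughing only in the hour before albuterol, and no timed cough record is stated for 0 to 120 minutes, so cough is an avoidable, secondary source of bias in the Aim 2 change and, through first-hour lapses, in Aim 1

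*Combined protocol and SAP*

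**What the plan says.** The synopsis (Study Description) states: "During the first hour of MCC imaging subjects will attempt to avoid coughing". Section 7.4 carries the same instruction, "During the first hour of MCC imaging patients will attempt to avoid coughing", and so does section 4.1 Treatment Design. None of them extends it to the second hour.

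The flow sheet in section 4.1 follows the same pattern. The pre-albuterol scan is labelled "5 MCC scan (no cough"), while the next two steps, "6 Albuterol MDI (4 puffs with spacer") and "7 MCC scan post albuterol", carry no such label. Coughs are first counted in the step after that, "8 PFT and directed coughing (30 coughs including any spontaneous induced by PFTs"), when the 120-minute imaging is over. The MCC procedure in section 8 has no cough instruction for either MCC hour.

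Section 9.1 defines clearance as 100 × (1 − retention) and averages the 10-minute values within each hour to give Ave60Clr and Ave120Clr. Section 9.3 uses Ave60Clr for Aim 1 and the within-subject change, Ave120Clr − Ave60Clr, for Aim 2. The covariates are age, gender and C/P. Cough has no covariate, handling rule or sensitivity analysis.

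**The concern.** Retention falls whether particles leave by ciliary transport or by cough. Aim 3 depends on cough clearing the same deposited particles, so the plan cannot treat cough before 120 minutes as harmless. Participants are asked to suppress cough before albuterol, and no such request is stated afterwards. Extra cough in the second hour would then add to the quantity that Aim 2 reads as a first estimate of albuterol's effect.

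The severe group is the most exposed in relative terms. Section 9.6 expects an Ave60Clr of 0.5 ± 0.25 and no albuterol response there, so a small absolute loss through cough is large beside the expected value. Without a cough record, a reader cannot tell how much of a small clearance is ciliary.

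**Working it through.** **Timing (flow sheet, section 4.1).** The pre-albuterol scan starts at cumulative minute 60 and lasts 64 minutes, the albuterol step lasts 6 and the post-albuterol scan lasts 54. In scan time these are 0–64, 64–70 and 70–124 minutes.

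**Averaging grid (section 9.1, as read here).** Ave60Clr is the mean of clearance at 10, 20, …, 60 minutes. Ave120Clr is the mean at 70, 80, …, 120 minutes. Time zero is the initial pair of images (section 8).

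**Effect of one cough.** A cough at time t that clears c% of initial activity adds c to every later image. Its share of each average is the fraction of that period's six images taken after t.

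| Cough at (min) | Share in Ave60Clr | Share in Ave120Clr | Share in the change |
|---|---|---|---|
| 5 | 6/6 | 6/6 | 0 |
| 35 | 3/6 | 6/6 | 3/6 |
| 55 | 1/6 | 6/6 | 5/6 |
| 64–70 | 0 | 6/6 | 6/6 |
| 95 | 0 | 3/6 | 3/6 |
| 115 | 0 | 1/6 | 1/6 |

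A cough before the first averaged image cancels out of the change. A cough between the first and the last averaged image raises it, in either hour.

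**Group-level illustration.** The documents give neither a cough rate nor a clearance per cough. Assume that 3 of 12 subjects cough once and that c is 0.5 or 2. Shift in the group mean = (3/12) × c × share.

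- Second-hour cough at 64–70, 95 or 115 minutes, shift in the Aim 2 change: 0.125, 0.06, 0.02 (c = 0.5); 0.50, 0.25, 0.08 (c = 2).
- First-hour cough at 5, 35 or 55 minutes, shift in Ave60Clr: 0.125, 0.06, 0.02 (c = 0.5); 0.50, 0.25, 0.08 (c = 2).
- The same first-hour coughs, shift in the Aim 2 change: 0, 0.06, 0.10 (c = 0.5); 0, 0.25, 0.42 (c = 2).

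If the boundary images at 0 and 60 minutes are averaged in as well (seven values per period), the second-hour shifts become 0.018–0.107 (c = 0.5) and 0.07–0.43 (c = 2).

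**Comparators (section 9.6).** The planned severe mean is 0.5. The planned mild response is 7.2 − 3.6 = 3.6. The largest shift, 0.50, equals the whole planned severe mean and is 0.50/3.6 = 14% of the planned mild response.

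**Drift with no cough and no albuterol effect.** Clearance accumulates, so Ave120Clr exceeds Ave60Clr whenever there is clearance in the first hour. Assume a constant rate in that hour. The mean image time is 35 minutes in the first hour and 95 in the second.

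- Mild: rate 3.6/35 = 0.103 per minute. If the rate continues, the change is 0.103 × 95 − 3.6 ≈ 6.2. If clearance stops at 60 minutes, it is 0.103 × 60 − 3.6 ≈ 2.6.
- Severe: rate 0.5/35 = 0.0143 per minute. The same two cases give 0.86 and 0.36.

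In the mild group the drift exceeds every cough shift above. In the severe group a 2% cough near the albuterol step (0.50) falls within the drift range, while a late one (0.08) is far below it. At 0.5% per cough every shift is below the drift range.

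**The case against.** **Existing safeguards.** Several provisions touch on cough. Section 5.2 excludes recent acute infection, including "Viral upper respiratory tract infection within 4 weeks of challenge". The screening call asks "Do you have a new or worsening cough", and a yes cancels the visit. Section 6.7 discontinues participants whose respiratory symptoms appear or worsen. Appendix 3 asks about cough and wheeze, and section 14 describes it as applying both before and during the study. These catch illness or a change in health. None yields a timed count of a participant's usual cough.

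**The images may show it.** A reader might infer that unrecorded cough is lost for good. That is too strong. Section 8 specifies consecutive 2-minute images continuing through the second hour, and a large abrupt loss could appear as a step. The with-and-without-outliers analysis in section 9.1 might also flag it. Neither can reliably attribute a loss to cough or detect small or widespread losses.

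**Group contrasts.** A reader might also infer that the mild–severe comparisons are biased. If both groups cough alike, the contribution cancels in expectation. Only differential cough biases the contrast, and the documents do not say which group coughs more. The effect on the Aim 1 test may also be slight. With one cough at 5 minutes in 3 of 12 severe subjects only, a simulated Welch test of mild against severe (planned means and SDs, 12 per group) has power 0.998 without cough, about 0.996 at 0.5% and about 0.98 at 2%. Welch is not the planned Tukey–Kramer comparison, so this is only a guide. This objection largely stands.

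**Already conceded.** Section 9.3 says that the pre-post comparison has no control and cannot establish efficacy. That stands, and recording cough would not change it. The concession does not mention cough, however, and does not extend to Aim 1.

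**Silence is not absence.** Section 11.9.1 says that case report forms are still to be developed from earlier templates. A cough log may exist, so the point is only that none is stated.

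**Conclusion.** The point holds as a secondary, inexpensively reduced source of bias. The stated cough instruction differs between the two periods that Aim 2 compares, and the outcome definition counts cough clearance as MCC. Within a group the direction is known: cough between the first and last averaged images inflates the Aim 2 change, and first-hour cough inflates Ave60Clr.

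The size is unknown. The 0.02 to 0.50 points for second-hour cough rest on three assumptions: 3 of 12 subjects coughing once, 0.5 to 2% cleared per cough, and the 10-minute grid above. The documents do not support reading cough as the main problem in Aim 2, since cumulative drift (about 2.6 to 6.2 points mild, 0.36 to 0.86 severe, also under assumptions) is generally larger. Nor do they support calling cough comparable with that drift throughout the severe group: at 2% this is true only of coughs early in the second hour.

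**What to change.** 1. Give the same cough-avoidance instruction for both MCC hours in the synopsis, section 4.1 (including flow-sheet step 7), section 7.4 and section 8.
2. Have the supervising staff record the time of each spontaneous cough from 0 to 120 minutes, including the albuterol step, on the case report form.
3. In section 9.3, report cough counts by group and hour beside the Aim 1 and Aim 2 results. Label any analysis that excludes coughers or adjusts for cough as exploratory: second-hour cough follows albuterol and may be affected by it, the no-cough subset is self-selected, and precision is low at 12 per group.

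The cost is protocol wording and one form item, since section 11.2 already has participants directly supervised during MCC measurements. The downside is a longer period of suppressing cough. If that is judged too burdensome, the timed tally alone still lets readers judge how much cough contributed.

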7.5. Phone Contact (Day Day X \pm Y)

N/A

7.6. Final Visit (Day Day X \pm Y)

N/A

7.7. Follow-Up Contact (Day Day 1 ± 3)

The study team will contact participants between 1 and 4 days after the study visit to confirm when study payment card has been loaded and to follow up on any questions or concerns.

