7.8. Premature Discontinuation

Study is considered completed after the last scan of the day. Subjects may withdraw at any time. Subjects may be withdrawn at any time for safety concerns. Subjects who have any unanticipated problems (UPs) with the study procedures will be monitored until resolution of the symptoms.

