10.3. Unanticipated Problems, Adverse Events, Serious Adverse Events

Definition of Adverse Event (AE) and Serious Adverse Event (SAE)

An adverse event for a given volunteer will be defined as failure of any of the safety criteria outlined above. Decrease in lung function (FEV1) greater than 20% will be considered an adverse event. Any symptoms that induce a volunteer to seek medical attention from any provider within 96 hours of a study visit will be considered an adverse event. A serious adverse event will be defined as any event that requires hospitalization or results in life threatening illness or injury, permanent (or likely to be permanent) illness or injury, or death if these events occur within 96 hours of a study visit (or if the clinical scenario leading up to hospitalization, illness, injury or death begins within 96 hours of a study treatment visit).

Grading criteria

In addition to determining whether an adverse event fulfills criteria for a serious adverse event or not, the severity of adverse events experienced by study participants will be graded according to the criteria set forth in the National Cancer Institute's Common Terminology Criteria for Adverse Events Version 4.0. This document (referred to herein as the NCI-CTCAE manual) provides a common language to describe levels of severity, to analyze and interpret data, and to articulate the clinical significance of all adverse events.

All adverse events whether or not listed in the NCI-CTCAE will be graded on a scale from 1 to 5 according to the following standards in the NCI-CTCAE manual (A semi-colon indicates 'or' within the description of the grade.):

Grade 1 = Mild; asymptomatic or mild symptoms; clinical or diagnostic observations only; intervention not indicated.

Grade 2 = Moderate; minimal, local or noninvasive intervention indicated; limiting age- appropriate instrumental ADL (preparing meals, shopping for groceries or clothes, using the telephone, managing money, etc.).

Grade 3 = Severe or medically significant but not immediately life-threatening; hospitalization or prolongation of hospitalization indicated; disabling; limiting self care ADL (bathing, dressing and undressing, feeding self, using the toilet, taking medications, and not bedridden).

Grade 4 = Life-threatening consequences; or urgent intervention indicated.

Grade 5 = Death related to AE.

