11.6. Safety Oversight

Data Safety Monitoring Plan: Data is initially recorded on paper documents, and the documents are maintained in a binder which is kept in a locked office within the Meadowmont/Eastowne or EPA Human Studies facility. Data will be stored in a secure facility with a guarded entrance and requires identification for entry. This data is then entered into REDCap by an initial data entry person and confirmed by a second user.

Medical Monitor

[name], has agreed to serve as an independent medical monitor (MM) for the human subjects studies associated with [name] RO1, titled "Functional Studies of Novel Genes Mutated in Primary Ciliary Dyskinesia II: Genotype to Phenotype". [name] is a Professor of Medicine, Division of Pulmonary Diseases and Critical Care Medicine, and the Associate Director of the Marsico Clinical and Translational Research Center, has experience with multiple clinical trials investigating mucociliary clearance in cystic fibrosis, and so is ideally suited to provide safety oversight for this project.

In regards to this proposal, the independent MM has the responsibility to 1) review and evaluate information relevant to the safety of the study. Specifically, this involves reviewing the protocols to be followed, including protocol halting rules, and addressing any safety concerns. 2) The MM will advise the protocol team on safety oversight. 3) The MM will be also be responsible for monitoring, collecting and reporting data related to unanticipated problems and adverse events.

In practice, the MM will review the protocols with the appropriate investigators before the studies begin. The MM will be notified of any unanticipated problems and adverse events immediately, and will report SAEs to the UNC IRB and to the NHLBI program officer within 48 hours. In the absence of any unanticipated problems and adverse events, the MM will review the protocol and results of the studies on a regular basis. Because of the irregular timing of subject recruitment, this may occur more frequently, but at least once yearly and after every 6 subjects complete the study.

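### Minor: adverse events count for 96 hours after the visit, but the only scheduled later contact may be made on day 1 and has no safety questions assigned to it

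*Combined protocol and SAP*

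**What the plan says.** Section 10.3 sets the counting window. An AE includes "Any symptoms that induce a volunteer to seek medical attention from any provider within 96 hours of a study visit". SAEs use the same 96 hours, and a later outcome also counts "if the clinical scenario leading up to hospitalization, illness, injury or death begins within 96 hours of a study treatment visit".

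On detection, Section 7.4 says "Adverse events are assessed at each visit", and there is one visit. Sections 7.5 (Phone Contact) and 7.6 (Final Visit) are marked not applicable, and Section 7.8 treats the study as complete after the day's last scan. That leaves Section 7.7: "The study team will contact participants between 1 and 4 days after the study visit". Its stated purposes are to confirm that the payment card is loaded and "to follow up on any questions or concerns".

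Appendix 3 holds four symptom and health-care questions and a fifth item that sends any positive answer to a study physician. Section 14 describes the appendix as serving the time before and during the study.

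Other safety provisions are:
- **Section 7.8:** "Subjects who have any unanticipated problems (UPs) with the study procedures will be monitored until resolution of the symptoms".
- **Section 11.6:** the Medical Monitor is "responsible for monitoring, collecting and reporting data related to unanticipated problems and adverse events", and "The MM will be notified of any unanticipated problems and adverse events immediately".
- **Section 11.2:** participants have an after-hours route to a study physician or a 24-hour line, and any SAE suspends the protocol pending IRB consultation.

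**The concern.** The window that decides what counts as an event is longer than the period the plan is sure to ask about. After the participant goes home there is one scheduled contact. It may fall on day 1, and its stated content is a payment matter plus an open prompt. A participant who sees an outside doctor on day 2 or 3 and does not mention it would have had an AE under Section 10.3 that the team need never hear of.

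What depends on this is safety oversight. Suspension on any SAE (Section 11.2), immediate notice to the Medical Monitor and onward SAE reporting within 48 hours (both Section 11.6) work only once the team knows of the event. The gap concerns the care-seeking AEs and the SAEs. The other AE criteria, such as a fall in FEV1 of more than 20%, are mainly observed on the visit day.

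**Working it through.** The plan gives no figure for this point, so there is none to reproduce. The check compares the two windows and does simple arithmetic.

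**Inputs**
- Counting window: 96 hours after the visit (Section 10.3).
- Permitted contact: 1 to 4 days after the visit (Section 7.7 text). Taking 1 day as 24 hours, this is 24 to 96 hours.
- Other scheduled post-visit contacts: none (Sections 7.5 and 7.6).
- Participants: 12 mild + 12 severe + 8 healthy = 32 (Section 9.2).
- Flow sheet in Section 4.1: albuterol is finished at cumulative minute 130, and the final scan ends at minute 433.

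**Timing.** Suppose the open prompt counts as an inquiry covering everything up to the contact. Hours with no later active contact = 96 − contact time.

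| Contact at | Hours left | Share of window |
|---|---|---|
| 24 h (day 1) | 96 − 24 = 72 | 75% |
| 48 h (day 2) | 96 − 48 = 48 | 50% |
| 72 h (day 3) | 96 − 72 = 24 | 25% |
| 96 h (day 4) | 96 − 96 = 0 | 0% |

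**Content.** If the open prompt is not counted, none of the 1 scheduled contacts has assigned AE questions in the text available. No structured inquiry then covers any of the 96 hours, whatever the day. This is an alternative reading to the table and must not be added to it.

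**Heading of Section 7.7.** It reads Day 1 ± 3, which is Day −2 (1 − 3) to Day 4 (1 + 3). The lower end falls before the visit, so it cannot match the text. The upper end is also unclear. Section 7.3 labels enrolment Day 0, which puts Day 4 at four days after the visit. The Table of Events labels the visit Day 1, which puts Day 4 at three days after, or 72 hours.

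**Time under observation.** From the end of albuterol dosing to the final scan is 433 − 130 = 303 minutes, about 5.05 hours. Events in that time are seen directly.

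**Cost of asking.** 32 × 4 = 128 recorded answers. Moving the call from 24 to 96 hours delays it by 96 − 24 = 72 hours.

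**The case against.** The sponsor has several fair replies.

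- **No contradiction.** A reader might infer that Sections 7.7 and 10.3 conflict. They do not. Section 10.3 classifies events and does not promise a call at hour 96, and every contact day in the text of Section 7.7 lies within the window. This stands.
- **The content gap may be only missing detail.** An open invitation to raise concerns is close to the first Appendix 3 question. Two of the four questions ask about the time since the last visit, which suits a post-visit call. The link is unstated rather than ruled out. This largely stands, and it is why the timing carries more of the weight.
- **The consent form was not available for review.** It may tell participants to report symptoms or medical care. This stands, so one cannot conclude that the plan gives no such instruction.
- **Other routes exist.** These are the 24-hour line, monitoring of known problems to resolution, the Medical Monitor's duties and regular reviews, and recruitment through the institution's own PCD clinics (Section 5.3). They narrow the gap but do not close it. Each depends on the participant reporting, on the event already being known, or on a clinic link that is likely but not guaranteed.
- **A 96-hour call is not complete either.** It cannot by itself capture a later hospitalization that grows out of a scenario starting within 96 hours, and it gives up some early detection. Both are true and belong with the fix.
- **Risk is low.** Section 10.2 describes the procedures as low risk, and Section 9 plans no AE analysis. This supports a minor rating.

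**Conclusion.** The point holds as a minor, inexpensive improvement to safety ascertainment. A fully compliant site can have no later active contact for up to 72 of the 96 hours in which events count, and no available text assigns the Appendix 3 questions to the one contact that exists.

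The 75% is the worst compliant day, and the best is 0%. It should not be read as 75% of events missed: these are hours, not events. The documents give neither an event rate nor a distribution of contact days, so the number missed cannot be estimated. Nor do the documents support saying that post-visit events go uncollected, since several routes remain open. The remaining exposure is to off-site events that participants do not volunteer. No MCC endpoint is affected.

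The conclusion assumes that a day means 24 hours from the end of the visit and that the consent form adds no scheduled contact.

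**What to change.** In Section 7.7:
1. Set the contact at or shortly after 96 hours from the end of the visit, and change the heading to match.
2. At that contact, ask and record the four Appendix 3 questions, all worded for the time since the study visit. Item 5 already sends any positive answer to a study physician.
3. Optionally, keep an early payment-card message and use it to ask participants to report symptoms or medical care promptly.

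The call replaces the planned one and needs no extra visit. Recording adds about 128 answers, and the early message adds up to 32 brief contacts. Without that message, an event that a day-1 call would have found may be learned of up to about 72 hours later. Later outcomes of scenarios that begin within 96 hours will still depend on the existing reporting routes.
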